4.8.1.1. Adverse Events and Serious Adverse Events

Adverse events (including serious adverse events (SAE), AEs causing permanent treatment discontinuation, deaths, and AEs of special interest) are recorded from the time of signed informed consent until the end of study. All AEs diagnosed by the Investigator will be reported and described.

All AEs will be dictionary coded by “lowest level term (LLT)”, “preferred term (PT)”, “high level term (HLT)”, “high level group term (HLGT)” and associated primary “system organ class (SOC)” using the version of MedDRA in effect at the time of the first database lock.

Adverse Event Observation Period

- Pre-treatment AEs are AEs that developed or worsened or became serious during the pre-treatment period.
- TEAEs are AEs that developed or worsened or became serious during the respective TEAE period.
- Post-treatment AEs are AEs that developed or worsened or became serious during the post-treatment period.

4.8.1.2. Adverse Events of Special Interest

Adverse events of special interest (AESI) are AEs (serious or non-serious) required to be monitored, documented, and managed in a pre-specified manner. AESIs will be recorded on the adverse event e-CRF using dedicated tick boxes, and/or identified using standard MedDRA queries (SMQ), company MedDRA queries (CMQ), MedDRA terms, and/or applicable laboratory assessments. [Appendix 10.3](#) contains the definitions used to identify AESIs:

The AESIs include:

- Anaphylactic reactions (e-CRF)
- General allergic events (SMQ)
- Moderate or severe infusion reactions (e-CRF)
- Hepatic Disorder (SMQ, lab data)
- Pregnancy (e-CRF)
- Symptomatic overdose with investigational medicinal product (e-CRF)
- Neurocognitive events (CMQ)
- New onset of diabetes (NOD) (lab data, HLT, and concomitant medications)
- Pancreatitis (e-CRF)

4.8.1.3. Events Causing Death

The observation periods for patient deaths are per the observation periods defined above.

- Death on-treatment: deaths occurring during the respective TEAE period,
- Death post-treatment: deaths occurring during the post-treatment period.

4.8.2. Laboratory Safety Variables

Clinical laboratory tests will consist of blood analyses (including hematology, clinical chemistry and other) and urinalysis. Clinical laboratory values will be converted and analyzed in both international units and US conventional units, with associated normal ranges provided by the

central laboratory. Both actual test values and “change from baseline” values (defined as the post-baseline value minus the baseline value) will be used in the result summaries. Potentially clinically significant values (PCSV) ranges will be applied to the laboratory test values as applicable (see [Appendix 10.4](#) for PCSV definitions). For those laboratory tests that do not have PCSV ranges, central laboratory normal ranges will be applied to identify out-of-range values. All laboratory test samples will be collected before study treatment administration during the protocol scheduled visits.

Unless otherwise specified below, blood samples for clinical laboratories will be collected at the protocol scheduled visits. The laboratory parameters (excluding those considered as efficacy parameters) will be classified as follows:

Hematology:

- Red blood cells and platelets: hemoglobin, hematocrit, erythrocytes count, platelets count, red blood indices
- White blood cells: white blood cells, neutrophils, lymphocytes, monocytes, basophils, eosinophils

Clinical chemistry:

- Metabolism: glucose, total protein, albumin, creatine phosphokinase
- Electrolytes: sodium, potassium, chloride, calcium, bicarbonate
- Renal function: creatinine, blood urea nitrogen (BUN), uric acid
- Liver function: Alanine aminotransferase (ALT), aspartate aminotransferases (AST), alkaline phosphatase (ALP), total bilirubin, LDH

Non-Efficacy Lipid Panel

HDL-C, TG, Apo A-1, Apo CIII, Apo E, and ratio Apo B/Apo A-1.

Urinalysis

Urinalysis will include the following parameters: color, clarity, pH, specific gravity, ketones, protein, glucose, blood, bilirubin, leukocyte esterase, nitrite, WBC, RBC, hyaline and other casts, bacteria, epithelial cells, crystals, and yeast.

Other

TSH, sex hormones (luteinizing hormone, follicle stimulating hormone, estradiol, and total testosterone).

4.8.3. Vital Signs

Vital signs parameters will include weight (kg or lb), height (cm or in), BMI (kg/m²), heart rate (bpm), respiration (rpm), temperature (C or F), systolic and diastolic blood pressure (mmHg) after resting at least five minutes. Both actual test values and “change from baseline” values (defined as the post-baseline value minus the baseline value) will be used in the result summaries. Potentially clinically significant values (PCSV) ranges will be applied to the vital sign parameter values as applicable (see [Appendix 10.4](#) for PCSV definitions).

BMI and height percentiles will be calculated (Cole, 1992; WHO, 2006; Rigby, 2004).

4.8.4. 12-Lead Electrocardiography (ECG)

A standard 12-lead ECG will be performed at specified time points according to [Appendix 10.7](#). The ventricular rate, PR, QRS, RR, QTcF, QTcB, and QT intervals will be recorded. Electrocardiogram assessments will be described as normal or abnormal.

4.8.5. Tanner stages

Tanner stage assessments will be performed at specified time points according to [Appendix 10.7](#). Tanner stages (1, 2, 3, 4, 5) will be recorded.

4.8.6. Physical Examination Variables

Physical examination will be conducted at the protocol scheduled visits (See [Appendix 10.7](#) for schedule of event). The result is an outcome of clinically significant (Yes/No, not examined).

4.9. Other Variables

Other assessment endpoints are listed and defined below. Protocol schedule visits will be assigned to the Global Analysis Windows (See [Appendix 10.2](#)).

- The change in hemoglobin A1c (HbA1c [%]) from baseline to post-baseline visits.
- The percent change in hs-CRP from baseline over time.
- The percent change in HDL-C from baseline over time.
- The change in carotid intima-media thickness (cIMT in mm) from baseline over time

4.10. Pharmacokinetic Variables

The PK variables are the concentrations of total evinacumab at each time point.

Total ANGPTL3 concentration in serum is a measure of target engagement by evinacumab and will be determined in the samples obtained to evaluate evinacumab concentration.

4.11. Immunogenicity Variables (ADA and NAb)

The immunogenicity variables are ADA status, titer, and neutralizing antibody (NAb) status for analyzed samples at time-point/visit. Serum samples for ADA will be collected at the clinic visits specified in [Appendix 10.2](#).

5. STATISTICAL METHODS

In general, patient data collected in Part A will be summarized for all patients (i.e., Part A Total). For Part B, data will be summarized again for all patients (i.e., Part B Total). Part C data summaries will show three columns, specifically, patients treated in Part A, patients treated in Part B, and Total. The baseline value is defined as the last available measurement prior to the date of the first study treatment administration regardless of the study treatment period.

In addition, pooled analyses will summarize data in three columns, specifically, Part A Patients, Part B Patients, and Total. The baseline value for the pooled analyses is defined as the last available measurement prior to the date of the first study treatment administration regardless of the study treatment period. Note: Although Part A patients only contributed data from Part C for the pooled analyses, Part A patient's baseline is defined as Part A baseline for variable derivations.

5.1. Demographics and Baseline Characteristics

Demographic and baseline characteristics will be descriptively summarized by total patients within each main study part (Part A or Part B). Parameters described in Section 4.1 will be summarized for patients in the SAF for Part A, and for patients in the ITT population for Part B.

Continuous data will be summarized using the number of patients with data, mean, SD, median, minimum and maximum. First quartile (Q1) and third quartile (Q3) will be also provided for baseline lipid parameters, HbA1c, and hs-CRP. Categorical and ordinal data will be summarized using the number and percentage of patients.

As applicable, other safety baseline data not listed in Section 4.1 will be presented collectively in the descriptive statistics summary tables containing respective post-baseline data.

For Part C safety analysis set, demographic and baseline characteristics will be summarized by total patients in Part C and by main study part (Part A or Part B) in which patients are originally enrolled at the beginning of the study.

Selected demographic and baseline characteristics will also be summarized for the pooled data in the pooled safety analysis set, by patient groups defined in Section 2.4.1.

5.2. Medical History

Medical history will be descriptively summarized by total patients within each main study part (Part A or Part B) and Part C. Parameters described in Section 4.2 will be summarized for patients in the SAF for Part A and C, and for patients in the ITT population for Part B. All reported patient's medical history will be presented by primary SOC and HLT. The tables will be presented by SOC sorted alphabetically and decreasing patient frequency of HLT based on the overall incidence in each main study part.

For patient disease characteristics, continuous data will be summarized using the number of patients with data, mean, SD, median, minimum and maximum. Categorical and ordinal data will be summarized using the number and percentage of patients.

5.3. Prior and Concomitant Medications

All prior medications, dictionary coded by WHO-DD, will be descriptively summarized by total patients within each main study part (Part A or Part B) for patients in the safety analysis set. Summaries will present patient counts (and percentages) for all prior medications, by decreasing frequency of the overall incidence of ATC followed by therapeutic class. In case of equal frequency across anatomic or therapeutic categories, alphabetical order will be used. Patients will be counted once in each ATC category (anatomic or therapeutic) linked to the medication, but may be counted several times for the same medication.

For patients in the safety analysis set, all concomitant medications during the respective treatment period, dictionary coded by WHO-DD, will be descriptively summarized by total patients within each main study part (Part A or Part B). Summaries will present patient counts (and percentages) for the concomitant medication groups described in Section 4.3 for all concomitant medications, by decreasing frequency of the incidence of ATC followed by therapeutic class. In case of equal frequency across anatomic or therapeutic categories, alphabetical order will be used. Patients will be counted once in each ATC category (anatomic or therapeutic) linked to the medication, hence may be counted several times for the same medication. Additionally, concomitant medications for LMT will be summarized by patient counts (and percentages) for the standardized medication names.

For Part C treatment period, concomitant medications will be dictionary coded by WHO-DD and will be descriptively summarized as described above. For patient in the Part C safety analysis set, medications will be summarized for all patients and by main study part (Part A or Part B) in which patients are originally enrolled at the beginning of the study. Summaries will present patient counts (and percentages).

Post-treatment medications will be dictionary coded by WHO-DD and will be provided in the study datasets.

5.4. Prohibited Medications

Listing of prohibited medications will be provided for the patients in the safety analysis set within main study part (Part A or Part B) and in the Part C safety analysis set during the extension (Part C).

5.5. Patient Disposition

Patient disposition includes the description of patient status at major milestone decisions in the study, as well as the patient analysis populations.

Patient study status for the main study part (Part A or Part B) will be summarized by total patients for the study (screened patients, screen failures, and non-enrolled but treated patients only). Summaries will provide the frequency (and percentage as applicable) of patients that met the criteria for the variables described in Section 4.5. Exception listings will be generated for any patient treated but not enrolled, and enrolled but not treated.

Patient analysis populations will be summarized by total patients within main study part (Part A or Part B), depicting frequencies (and percentages) of patients that met the criteria for each population described in Section 3.

For Part C treatment period, the patient study status and patient analysis populations will be summarized for all patients and by main study part (Part A or Part B) in which patients are originally enrolled at the beginning of the study on the Part C safety population for the variables described in Section 4.5.

The incidence of premature study treatment discontinuation (irrespective of the reason) and premature treatment discontinuation due to AEs will be presented graphically by total patients within Part B, or Part C in the respective safety analysis set using the Kaplan-Meier method.

5.6. Extent of Study Treatment Exposure and Compliance

The extent of study treatment exposure for the main study part (Part A or Part B) described in Section 4.6 will be assessed and summarized for all patients in the safety analysis set.

The extent of study treatment exposure for Part C described in Section 4.6 will be assessed and summarized for patients in the Part C safety analysis set, specifically for all patients and again by main study part (Part A or Part B) in which patients are originally enrolled at the beginning of the study.

The extent of study treatment exposure on the pooled data described in Section 4.6 will be assessed and summarized in the pooled safety analysis set by patient groups.

5.6.1. Exposure to Investigational Product

Study treatment exposure in the respective treatment period will be descriptively summarized for treatment duration, total number of infusions, and observation period duration (Part A) as described in Section 4.6. Treatment duration and total number of infusions will be summarized using the number of patients with data, mean, SD, median, minimum and maximum.

5.6.2. Study Treatment Compliance

Both monitored and derived protocol deviations will be summarized for important deviation categories by count (percentage), and again by type of important deviation (patient count and percentage). A patient listing of all important and minor protocol deviations will be provided.

Descriptive statistics of the infusion frequency of study treatment will be summarized. Further, study treatment infusion interruptions and incomplete infusions with reason will be summarized by patient count (percentage) and a patient listing will be provided for those patients with incomplete infusions. Cases of study treatment overdose will be reported in the AE e-CRF page and will be described in the adverse event analysis.

5.7. Analyses of Efficacy Variables

For statistics where international and conventional units do not impact the results (e.g. means and least square (LS) means for percent changes from baseline, rates of patients below a threshold), derivations will be calculated and statistical models will be run using conventional units. For other statistics (e.g. descriptive statistics at baseline and over time, absolute changes from baseline), derivations will be presented in both international and conventional units.

Statistical analyses for the primary efficacy endpoint and secondary efficacy endpoints will be conducted in Part B as described below, and will be completed during the step 2 efficacy analyses (Section 7). Remaining descriptive efficacy analyses will be completed during step 3.

5.7.1. Analysis of Primary Efficacy Variable for Part B

While applying the ITT estimand, the percent change from baseline in calculated LDL-C at week 24 will be descriptively summarized for all patients in the ITT population using mean, SE, and 95% CI. Missing data will be imputed using a pattern mixture model (PMM) approach as described below (see Appendix 10.6 for more details).

In the PMM approach, different imputation strategies will be applied to calculated LDL-C values missing during the on-treatment period (i.e., within the time period from the first study treatment administration up to the day of last study treatment administration +35 days in Part B) versus calculated LDL-C values missing due to treatment discontinuation after the on-treatment period (i.e., after the day of last study treatment administration +35 days in Part B) based on the following assumptions:

- Patients within 35 days of their last study treatment administration in Part B would continue to show benefit from treatment similar to that observed at the scheduled time point. Therefore, calculated LDL-C values missing during the on-treatment period (e.g., samples obtained out-side the specified window for apheresis, no blood sample available although visit was performed, etc.) should be considered “Missing at Random” and imputed based on other observed measurements in the on-treatment period.
- Patients who stopped taking their study treatment in Part B no longer benefited from it after discontinuation, and thus tended to have calculated LDL-C values returning to baseline. Therefore, calculated LDL-C values missing after the on-treatment period should be imputed based on patient’s own baseline value.

Missing data from the ITT population will be imputed 100 times to generate 100 complete data sets, using the SAS MI procedure (using Markov Chain Monte Carlo). The 100 completed datasets of observed and imputed calculated LDL-C data will be used for the primary analysis.

For the percent change from baseline calculated LDL-C endpoint, the 100 complete datasets of observed and imputed calculated LDL-C data at week 24 will be analyzed using the SAS MEANS procedure. The SAS MIANALYZE procedure will be used to generate valid statistical inferences by combining results from the 100 analyses using Rubin’s formulae. Combined estimate for mean at Week 24 will be provided with the standard error (SE) and 95% confidence interval (CI). Formal statistical testing is not planned.

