11.2. Justification of Sample Size

Since this is an open-label single treatment arm study, formal statistical testing is not planned. Therefore, a calculation for patient sample size is not applicable.

Six patients are planned to be enrolled for Part A and 14 pediatric patients are planned to be enrolled for Part B, considering the recruitment constraints in this rare patient population.

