2.2. Sample Size and Power Considerations

Since this is an open-label single treatment arm study, formal statistical testing is not planned. Therefore, a calculation for patient sample size is not applicable.

[figure not shown]
Six patients are planned to be enrolled for Part A and 18 pediatric patients are planned to be enrolled for Part B, considering the recruitment constraints in this rare patient population.

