4.7.1. Primary Efficacy Variable (s)

The primary efficacy endpoint for Part B is:

- The percent change in calculated LDL-C from baseline to week 24 (intent-to-treat [ITT] estimand) in Part B. The primary endpoint is defined as: $100 \times (\text{calculated LDL C value at week 24} - \text{calculated LDL-C value at baseline}) / \text{calculated LDL-C value at baseline}$.

The baseline LDL-C value is defined as the last calculated LDL-C value obtained before the first dose of study treatment in Part B. The calculated LDL-C at week 24 will be the LDL-C value obtained within the week 24 analysis window.

The intent-to-treat estimand used for the primary efficacy analysis is the treatment policy strategy, specifically the occurrence of the intercurrent events is irrelevant; the value for the primary efficacy endpoint is used regardless of whether or not the intercurrent events occur. The intent-to-treat estimand for the primary efficacy analysis is defined as:

- A. The patient population is defined as the Intent-to-treat population (Section 3.1.1).
- B. The primary efficacy endpoint is defined above.
- C. The intercurrent events of interest are the administration of study treatment and the administration of subsequent therapies. The interruption of study treatment and the change in subsequent therapies are ignored, and the value for the primary efficacy endpoint is used regardless of adherence to study treatment and subsequent therapies.
- D. The population-level summary for the primary efficacy endpoint is evinacumab mean value, SE and 95% confidence interval.

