4.7.2. Secondary Efficacy Variable(s)

The secondary continuous efficacy endpoints in Part B are provided below, applying the ITT estimand described for primary efficacy endpoint (Section 4.7.1 definitions A, C and D).

- The percent change in Apo B from baseline to week 24 (ITT estimand)
- The percent change in non-HDL-C from baseline to week 24 (ITT estimand)
- The percent change in TC from baseline to week 24 (ITT estimand)
- The percent change in calculated LDL-C from baseline to week 24 in patients who have negative/negative and null/null mutations (ITT estimand)
- The percent change in Lp(a) from baseline to week 24 (ITT estimand)
- The absolute change in LDL-C at week 24 (ITT estimand)

The secondary binary efficacy endpoint in Part B is provided below, applying the ITT estimand described for primary efficacy endpoint (Section 4.7.1 definitions A and C). The definition for the population-level summary (definition D) is evinacumab proportion and 95% confidence interval.

- The proportion of patients with $\geq 50\%$ reduction in calculated LDL-C at week 24 (ITT estimand)

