5.7.1.1. Sensitivity of the Primary Efficacy Analysis

Robustness of the primary analysis statistical method will be assessed through sensitivity analyses, including an ITT analysis and an on-treatment analysis of the percent change in calculated LDL-C from baseline to week 24 using a mixed-effect model with repeated measures (MMRM) approach.

Sensitivity to Non-Good Clinical Practice (GCP) Compliant Sites

To assess the impact of non-GCP compliance sites on the primary efficacy endpoint, the primary efficacy analysis will be performed excluding non-GCP compliant sites. Sites known to be non-GCP compliant at the time of database lock will be identified for this analysis before database lock. Any additional sites determined to be non-GCP compliant post-database lock will be separately identified.

Sensitivity to the Handling of Missing Data

Sensitivity analyses will be conducted to assess the robustness of the primary efficacy analysis with regards to the handling of missing data ([Little RJ 2012](#)).

Mixed-effect Model with Repeated Measures (MMRM) Approach

The percent change from baseline in calculated LDL-C at week 24 will be analyzed in the ITT population using a mixed effect model with repeated measures (MMRM) approach. All post-baseline data available within week 1 to week 24 analysis windows regardless of adherence to treatment and subsequent therapies will be used and missing data are accounted for by the MMRM model. The MMRM model assumes “missing-at-random” (MAR). The model will include the fixed categorical effect of time point (weeks 1, 2, 4, 8, 12, 16, 20, and 24), as well as the continuous fixed covariates of baseline calculated LDL-C value.

This model will be run using Statistical Analysis Software (SAS) mixed procedure with an unstructured correlation matrix to model the within-patient errors. Parameters will be estimated using restricted maximum likelihood method with the Newton-Raphson algorithm. Denominator degrees of freedom will be estimated using Satterthwaite’s approximation. This model will provide baseline adjusted least-squares mean estimate at week 24 with their corresponding standard error.

Sensitivity to On-treatment Calculated LDL-C Values

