5.7.2.1. Continuous Endpoints Anticipated to have a Normal Distribution

Continuous secondary variables defined in Section 4.7.2 anticipated to have a normal distribution (i.e. lipids other than Lp(a)) will be analyzed using the same ITT estimand and PMM approach for missing data as described for the primary efficacy endpoint.

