10.6. Detailed Description of Pattern Mixture Model

As the primary analysis of the primary efficacy endpoint (i.e., percent change from baseline to week 24 in calculated LDL-C for Part B), a pattern-mixture model approach will be used with a different imputation strategy applied for missing calculated LDL-C values during the on-treatment period (i.e., within the time period from the first study treatment administration up to the day of the last study treatment administration +35 days or to the day before the first long-term extension treatment administration, whichever comes first for Part B) and missing LDL-C values after treatment discontinuation (i.e., after the day of last study treatment administration +35 days in Part B) based on the following assumptions:

- Patients within 35 days of their last study treatment administration in Part B would continue to show benefit from treatment similar to that observed at the scheduled time point. Therefore, calculated LDL-C values missing during the on-treatment period will be considered “Missing at Random” and imputed using a model estimated using all samples collected on treatment.
- Patients who stopped taking their study treatment no longer benefited from it in the future, and thus tended to have calculated LDL-C values returning to baseline. Thus calculated LDL-C values missing after treatment discontinuation will be imputed based on patient’s own baseline value.

The assumptions for this approach are based on the following considerations:

- Missing values during the on-treatment period are mostly consecutive to:
 - Visits performed outside of the pre-specified time-window
 - No blood sample available although visit was done
 - LDL-C not measurable due to technical reasons

In addition, these missing data are often intermittent, i.e., followed by LDL-C values collected at subsequent visits. It is therefore considered reasonable to assume that these missing data were “At Random”.

Missing LDL-C values will be imputed 100 times to generate 100 complete data sets. The percent change from baseline to week 24 will be derived from observed and imputed LDL-C at this time point. The completed data sets will be analyzed using the SAS MEANS procedure. The results from the 100 analyses will be combined using Rubin’s formulae. If necessary, the number of imputations (100) will be increased until stable estimates are obtained.

Imputation of missing data during the on-treatment period

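### The primary 95% CI is pooled by Rubin's formulae with no complete-data degrees of freedom; as written it covers about 93% with 14 or 18 patients

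*SAP*

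**What the plan says.** SAP 5.7.1 and Protocol 11.4.3.1 impute missing week-24 LDL-C 100 times, summarise each completed data set with PROC MEANS, and pool: "The SAS MIANALYZE procedure will be used to generate valid statistical inferences by combining results from the 100 analyses", by Rubin's formulae. SAP 10.6 repeats the route ("The completed data sets will be analyzed using the SAS MEANS procedure"), as does Protocol Appendix 1. These appendices give seeds, minimum values, imputation variables and sample code. None of the four places gives complete-data degrees of freedom, an EDF value or a small-sample adjustment.

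The interval is part of the estimand in SAP 4.7.1: "The population-level summary for the primary efficacy endpoint is evinacumab mean value, SE and 95% confidence interval".

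The SAP does name a df method for the MMRM sensitivity analysis (SAP 5.7.1.1): "Denominator degrees of freedom will be estimated using" Satterthwaite's approximation.

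The planned size of Part B differs between the documents. SAP 2.2 says "18 pediatric patients are planned to be enrolled for Part B" and Protocol 11.2 (Amendment 2) says "14 pediatric patients are planned to be enrolled for Part B".

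The same pooling route is used for the continuous secondary endpoints other than Lp(a), which "will be analyzed using the same ITT estimand and PMM approach for missing data as described for the primary efficacy endpoint" (SAP 5.7.2.1). One of these is the LDL-C change "in patients who have negative/negative and null/null mutations" (SAP 4.7.2). SAP 5.7.1.2 uses it for the subgroups as well.

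**The concern.** Rubin's original df formula is a large-sample result. It reflects the finite number of imputations and treats the within-imputation variance as known. Here that variance is estimated from 14 or 18 children, so a mean and its SE carry n-1 = 13 or 17 df at most. If the pooled interval uses Rubin's df, it takes what is in effect a normal multiplier and is too short.

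This has an odd consequence. If every week-24 value is observed, the planned route gives a narrower interval than the ordinary t interval from the same numbers.

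No hypothesis test is planned, so this CI is the only interval statement attached to the primary result, and the Part B analysis may go into a submission dossier (SAP 7.2). The shortfall grows as n falls, so it is largest in the receptor-negative and null/null subset and in the subgroups.

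**Working it through.** **Inputs.** From the documents: two-sided 95% level and m = 100 imputations (SAP 5.7.1), n = 14 (Protocol 11.2) or 18 (SAP 2.2). The documents calculate no coverage or interval width, so there is no figure of theirs to reproduce; the benchmark is the nominal 95%. Assumed: normal percent changes, the amount of missing data, the SD and the subset sizes.

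**Rubin's df.** df = (m-1)/λ², where λ is the between-imputation share of the total variance.

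- λ cannot exceed 1, so df is at least 99, with multiplier t(99) = 1.984.
- λ = 0.02: 99/0.0004 = 247,500. λ = 0.10: 99/0.01 = 9,900. The multiplier is 1.960 in both cases.
- As λ goes to 0, df goes to infinity and the multiplier is 1.960.

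The number of patients does not enter the formula.

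**Coverage with nothing missing** (exact for normal data) is P(|t with n-1 df| < 1.960).

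| n | correct multiplier | coverage with 1.960 | CI too narrow by |
|---|---|---|---|
| 14 | t(13) = 2.160 | 92.8% | 1 - 1.960/2.160 = 9.3% |
| 18 | t(17) = 2.110 | 93.3% | 1 - 1.960/2.110 = 7.1% |

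**In percentage points.** Take the mean of -47% from the adult and adolescent study (Protocol 1) and an assumed SD of 15 to 30 points. Each limit moves by (t - 1.960) × SD/√n:

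- n=14: 0.200 × 4.01 = 0.8 to 0.200 × 8.02 = 1.6 points
- n=18: 0.150 × 3.54 = 0.5 to 0.150 × 7.07 = 1.1 points

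**Small-sample df for comparison (Barnard-Rubin).** With ν = n-1, ν_obs = ((ν+1)/(ν+3)) × ν × (1-λ), and 1/df = 1/(Rubin df) + 1/ν_obs.

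- n=14, λ=0.02: ν_obs = (14/16) × 13 × 0.98 = 11.15, so df = 11.1. At λ=0.10, df = 10.2.
- n=18, λ=0.02: ν_obs = (18/20) × 17 × 0.98 = 14.99, so df = 15.0. At λ=0.10, df = 13.8.

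**Simulation with missing values.**

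- *Missing at random:* 1 to 3 week-24 values missing, proper normal imputation from one covariate correlated 0.5 or 0.8 with the outcome, m = 100, 10,000 replicates per setting. Rubin's df covered 92.9% to 94.1% at n=14 and 93.4% to 94.0% at n=18. With EDF=n-1, coverage was about 95.5% to 96.6%.
- *Return to baseline:* 5% to 10% discontinuing, all with week 24 missing, SD 20, 8,000 replicates. Coverage was 93.7% to 93.8% at n=14 and 94.2% to 94.4% at n=18 without EDF, and 95.6% to 95.9% with it.

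**Subsets.** The documents give no subset sizes. If a subset had 3, 4, 5 or 6 patients and nothing were missing, the 1.960 interval would cover 81.1%, 85.5%, 87.8% or 89.3%.

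**The case against.** The strongest reply is that the result is conditional. The text names MIANALYZE and Rubin's formulae but does not forbid EDF, so a programmer could supply n-1 and still comply. That is true, but nothing in the text asks for it, and the rule as stated leads to the short interval.

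The other objections bear on size:

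- *The interval is descriptive.* There is no test and no success threshold, and each limit moves by 1.6 points at most in the illustration above, around an expected reduction near 47%. This stands, and it limits the severity.
- *The observed-data table in SAP 5.7.3 gives n, mean and SD at week 24.* With complete data a reader could rebuild the t interval from it. This limits the harm but leaves the reported CI uncorrected.
- *The MMRM comparison is weak.* SAP 5.7.1.1 promises only a least-squares mean and SE for that model, with no interval. This is fair; the comparison shows only that df were considered elsewhere.
- *The subset sizes are assumed, and SAP 5.7.1.2 runs subgroups only where numbers allow.* This also stands, but that condition does not cover the receptor-negative and null/null secondary endpoint.
- *Shortfalls are smaller under return-to-baseline imputation.* They are, at roughly 94% coverage, but still below nominal.

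**Conclusion.** The point holds. No complete-data df is stated in either document, and Rubin's formulae as written give a multiplier of 1.96 to 1.98 whatever the number of patients. With complete data the nominal 95% interval covers 92.8% (n=14) or 93.3% (n=18). In the simulations with some values missing it covers about 93% to 94%.

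The complete-data figures are exact for normal percent changes. The simulated ones rest on the assumed correlations, SDs and missingness patterns, and the subset figures on assumed sizes.

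This should be fixed, because the interval is part of the defined primary summary and is too short under the stated rule. It is a modest precision error and does not put the conclusion on LDL-C reduction at risk.

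**What to change.** Add to SAP 5.7.1, 5.7.1.2 and 5.7.2.1:

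> MIANALYZE is run with complete-data df equal to the number of patients analysed minus 1 (EDF=n-1, Barnard-Rubin). When no week-24 value in the analysed set is missing, the ordinary t interval with n-1 df is reported.

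The second sentence is needed because EDF=n-1 does not return t(n-1) as missingness vanishes. Its df tends to n(n-1)/(n+2). At n=14 that is 14 × 13/16 = 11.4 df, a multiplier of 2.19 against 2.16. At n=3 it is 3 × 2/5 = 1.2 df, a multiplier of 8.65 against 4.30.

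The cost is one procedure option and two sentences. Relative to the 1.960 interval, the primary CI becomes 10.2% wider (n=14) or 7.6% wider (n=18) with nothing missing, and 12.1% or 8.8% wider at λ = 0.02.

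In very small subsets with some missing data the rule is conservative. With negligible missingness the multiplier is 4.30 against t(3) = 3.18 at n=4, and 2.85 against t(5) = 2.57 at n=6. The SAP should say so where those intervals are reported. The SAP needs revising in any case, since it reflects Protocol Amendment 1 and still plans 18 patients for Part B.
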